10.4.4 Retention of Documentation

All study-related correspondence, patient records, consent forms, patient privacy documentation, records of the distribution and use of all investigational products, and copies of eCRFs should be maintained on file.

For countries falling within the scope of the ICH guidelines, the Allergan-specific essential documents should be retained until at least 2 years after the last approval of a marketing application in an ICH region and until there are no pending or contemplated marketing applications in an ICH region or at least 2 years have elapsed since the formal discontinuation of clinical development of the investigational product. These documents should be retained for a longer period, however, if required by the applicable regulatory requirement(s) or if needed by Allergan.

In addition, for countries not falling within the scope of the ICH guidelines, local regulatory requirements should be followed regarding the retention of clinical study documentation.

Allergan requires that it be notified in writing if the investigator wishes to relinquish ownership of the data so that mutually agreed-upon arrangements can be made for transfer of ownership to a suitably qualified, responsible person.

10.5 Labeling, Packaging, and Return or Disposal of Study Medications/Treatments

10.5.1 Labeling/Packaging

The study medication will be packaged and supplied by Allergan. The medication will be identified as an investigational compound.

The study medication will be provided in sealed study kits containing 2 multidose bottles of study treatment; 1 bottle will be labeled Dominant ([REDACTED]) and 1 bottle will be labeled Non-Dominant ([REDACTED]). The study number and kit number, at a minimum, will be printed on the outer carton and bottle labels. Additional labeling will be in accordance with local regulations.

10.5.2 Clinical Supply Inventory

The investigator must keep an accurate accounting of the number of investigational units received from Allergan, dispensed or administered to the patients, the number of units returned to the investigator by the patient (if applicable), and the number of units returned to

Allergan during and at the completion of the study. A detailed inventory must be completed for the study medication. The study medication must be dispensed or administered only by an appropriately qualified person to patients in the study. The medication is to be used in accordance with the protocol for patients who are under the direct supervision of an investigator. A unit is defined as a study kit that is comprised of 2 multidose bottles of study medication.

10.5.3 Return or Disposal of Study Medications/Treatments and/or Supplies

All clinical study medications/treatments and/or supplies will be returned to Allergan or Allergan's designee for destruction.

10.6 Monitoring by the Sponsor

A representative of Allergan will monitor the study on a periodic basis. The determination of the extent and nature of monitoring will be based on considerations such as the objective, purpose, design, complexity, blinding, size, and endpoints of the study.

Authorized representatives of Allergan or regulatory authority representatives will conduct onsite visits to review, audit and copy study-related documents. These representatives will meet with the investigator(s) and appropriate staff at mutually convenient times to discuss study-related data and questions.

10.7 Publications

Allergan, as the sponsor, has proprietary interest in this study. Authorship and manuscript composition will reflect joint cooperation between multiple investigators and sites and Allergan personnel. Authorship will be established prior to the writing of a manuscript. As this study involves multiple centers, no individual publications will be allowed prior to completion of the final report of the multicenter study except as agreed with Allergan.

12.2 Package Insert

The appropriate package insert will be supplied to investigators in countries where the product is marketed.

12.3 Glossary of Abbreviations

Term/Abbreviation	Definition
5-HT	serotonin
ANCOVA	analysis of covariance
AP	analysis plan
AUC	area under the plasma concentration-time curve
AUC ₀₋₁₂	area under the plasma concentration-time curve from time 0 to 12 hours
AUC _{0-inf}	area under the plasma concentration-time curve from time 0 to infinity
AUC _{0-tlast}	area under the plasma concentration curve from time 0 to the last timepoint
BID	twice daily
bpm	beats per minute
C _{max}	plasma maximum concentration
C/D	cup to disc
cd/m ²	candelas per square meter
CFR	Code of Federal Regulations
CMH	Cochran-Mantel-Haenszel
CNS	central nervous system
D	diopters
DET	dry eye test
EC ₅₀	maximal effective concentration
ECGs	electrocardiograms
eCRF	electronic case report form
EDC	electronic data capture
EU	European Union
FDA	Food and Drug Administration
GCP	Good Clinical Practices
GLP	Good Laboratory Practice
HCl	hydrochloride
HIPAA	Health Insurance Portability and Accountability Act Standards for Privacy of Individually Identifiable Health Information
ICH	International Conference on Harmonisation
IEC	Independent Ethics Committee
IOLs	intraocular lenses

IOP	intraocular pressure
IRB	Institutional Review Board
IxRS	interactive response system
LASIK	laser-assisted in situ keratomileusis
LC-MS/MS	liquid chromatography tandem mass spectrometry
MAOIs	monoamine oxidase inhibitors
MedDRA	Medical Dictionary for Regulatory Activities
mITT	modified intent-to-treat
NDA	New Drug Application
NEI VFQ-25	National Eye Institute Visual Function Questionnaire 25
NOAEL	no-observed-adverse-effect-level
NVPT	near vision task-based presbyopia
NZW	New Zealand White
OCT	Optical Coherence Tomography
OD	right eye
OS	left eye
OTC	over-the-counter
OU	both eyes
PDE5	phosphodiesterase 5
PGIC	Patient Global Impression of Change
PIOL	phakic intraocular lens
PRK	photorefractive keratectomy
PRO	patient-reported outcome
QD	once daily
RK	radial keratotomy
SEB	scleral expansion band
T _{1/2}	half-life
UDVA	uncorrected distance visual acuity
UNVA	uncorrected near visual acuity
US	United States
VAS	visual analog scale
w/v	weight/volume

12.4 Protocol Amendment 1 Summary

Title: A Phase 2, Multicenter, Double-Masked, Randomized, Vehicle-Controlled, Parallel Group Study Evaluating the Safety, Efficacy, and Pharmacokinetics of the Fixed Combination of AGN 199201 and AGN 190584 in Patients With Presbyopia

Protocol 199201-010 Amendment 1

Date of Amendment: February 2016

Amendment Summary

This summary includes changes made to Protocol 199201-010 (October 2015). Grand Seiko autorefractor is no longer a mandated method for pupil diameter measurement, since not all sites have this autorefractor. Only selected sites will use this measurement.

Following is a summary of content-oriented changes that were made to each section of the protocol, and a brief rationale for these changes. Minor editorial and document formatting revisions have not been summarized.

Section	Revision	Rationale
Title Page	The Allergan Signatory was changed, an e-mail address was added for serious adverse event reporting, and the Allergan Medical Safety Physician contact information was changed	To reflect the current Therapeutic Area Head and Safety Physician and to facilitate serious adverse event reporting
[REDACTED]	[REDACTED]	[REDACTED]
[REDACTED]	[REDACTED]	[REDACTED]
[REDACTED]	[REDACTED]	[REDACTED]
[REDACTED]	[REDACTED]	[REDACTED]
[REDACTED]	[REDACTED]	[REDACTED]
[REDACTED]	[REDACTED]	[REDACTED]
[REDACTED]	[REDACTED]	[REDACTED]
[REDACTED]	[REDACTED]	[REDACTED]
[REDACTED]	[REDACTED]	[REDACTED]

Approval Date: 18-Aug-2016

Section	Revision	Rationale
[REDACTED]	[REDACTED]	[REDACTED]
[REDACTED]	[REDACTED]	[REDACTED]
[REDACTED]	[REDACTED]	[REDACTED]
Section 4.5.1.1	
If a female becomes pregnant during the study, the investigator will notify the sponsor immediately after the pregnancy is confirmed, and the patient will be exited from the study after appropriate safety follow up. The investigator will (1) notify the patient's physician that the patient was enrolled in this study and treated with an investigational drug ocular oxymetazoline, ocular pilocarpine, or the combination of oxymetazoline and pilocarpine, and (2) follow the progress of the pregnancy. The investigator must document the outcome of the pregnancy and provide a copy of the documentation to Allergan.
	To be consistent with the Informed Consent Form
Section 5.7	Text referring to a temperature monitoring device was deleted	To apply to sites that may not have a temperature monitoring device
[REDACTED]	[REDACTED]	[REDACTED]

Approval Date: 18-Aug-2016

Section	Revision	Rationale
[REDACTED]	[REDACTED]	[REDACTED]
[REDACTED]	[REDACTED]	[REDACTED]
[REDACTED]	[REDACTED]	[REDACTED]
[REDACTED]	[REDACTED]	[REDACTED]
[REDACTED]	[REDACTED]	[REDACTED]
Section 8.5	Deleted instruction for patients to remain at the study site for the duration of the visit	To minimize patient inconvenience
Section 9.5	This section was added to describe the procedures for pregnancy follow-up and reporting	To be consistent with the Informed Consent Form

Approval Date: 18-Aug-2016

12.5 Protocol Amendment 2 Summary

Title: A Phase 2, Multicenter, Double-Masked, Randomized, Vehicle-Controlled, Parallel Group Study Evaluating the Safety, Efficacy, and Pharmacokinetics of the Fixed Combination of AGN-199201 and AGN-190584 in Patients With Presbyopia

Protocol 199201-010 Amendment 2

Date of Amendment: March 2016

Amendment Summary

This summary includes changes made to Protocol 199201-010 Amendment 1 (February 2016). The order of the Grand Seiko automated refraction was corrected in Table 2, the description of the primary efficacy variable was clarified, and selected sites are now to use only the Zeiss Visante OCT model.

Following is a summary of content-oriented changes that were made to each section of the protocol, and a brief rationale for these changes. Minor editorial and document formatting revisions have not been summarized.

Section	Revision	Rationale
Protocol Summary, Key Inclusion Criteria	
 Natural or corneal laser refractive surgery corrected [REDACTED] presbyopia in each eye and subjective complaints of poor near vision that impact activities of daily living, [REDACTED] 	For clarification
Protocol Summary, Efficacy, and Section 7.2.1	The primary efficacy variable will be the weighted average change from baseline in mesopic, high contrast UNVA lines at day 28 in the nondominant eye.	For clarification

Approval Date: 18-Aug-2016

Section	Revision	Rationale
	[Redacted]	
	[Redacted]	[Redacted]
[Redacted]	[Redacted]	[Redacted]
	[Redacted]	[Redacted]
	[Redacted]	[Redacted]
[Redacted]	[Redacted]	[Redacted]
[Redacted]	[Redacted]	[Redacted]
[Redacted]	[Redacted]	[Redacted]
	[Redacted]	[Redacted]
	[Redacted]	[Redacted]
[Redacted]	[Redacted]	[Redacted]
	[Redacted]	[Redacted]
	[Redacted]	[Redacted]

Approval Date: 18-Aug-2016

Section	Revision	Rationale
[REDACTED]	[REDACTED]	[REDACTED]
[REDACTED]	[REDACTED]	[REDACTED]
[REDACTED]	[REDACTED]	[REDACTED]
[REDACTED]	[REDACTED]	[REDACTED]
Section 8.5	
Patients must not read, use the computer, or look at cell phones/tablets without the use of reading glasses during any portion of the study visits. Note: Patients will be required to refrain from using their glasses during the near-vision tasks and associated near-vision task questionnaires, but may use their glasses to fill out other study-related questionnaires.	For clarification

Approval Date: 18-Aug-2016

12.6 Protocol Amendment 3 Summary

Title: A Phase 2, Multicenter, Double-Masked, Randomized, Vehicle-Controlled, Parallel-Group Study Evaluating the Safety, Efficacy, and Pharmacokinetics of the Fixed Combination of AGN-199201 and AGN-190584 in Patients With Presbyopia

Protocol 199201-010 Amendment 3

Date of Amendment: June 2016

Amendment Summary

This summary includes changes made to Protocol 199201-010 Amendment 2 (March 2016). Mesopic and photopic DCNVA in the nondominant eye was added at baseline and day 28, and a statement was added that the investigator should note if the pupil dilated normally after the fundusoscopic examination at screening and visit 6.

Following is a summary of content-oriented changes that were made to each section of the protocol, and a brief rationale for these changes. Minor editorial and document formatting revisions have not been summarized.

Section	Revision	Rationale
[REDACTED]	[REDACTED]	[REDACTED]
[REDACTED]	[REDACTED]	[REDACTED]
[REDACTED]	[REDACTED]	[REDACTED]
[REDACTED]	[REDACTED]	[REDACTED]

Approval Date: 18-Aug-2016

Section	Revision	Rationale
[REDACTED]	[REDACTED]	[REDACTED] d
Section 7.3.1	A detailed algorithm for the derivation of the primary efficacy variables will be documented in the AP.	For clarification
[REDACTED]	[REDACTED]	[REDACTED]
Section 7.4	Subgroup analyses will be performed for the primary efficacy variable by UNVA at baseline (20/40 to 20/80 and 20/100 to 20/200), age group, and iris color (brown or not brown), gender, race, and ethnicity.	Gender, race, and ethnicity subgroup analyses will not be performed
Sections 8.4.2 [REDACTED]	[REDACTED]	[REDACTED]

Approval Date: 18-Aug-2016

ALLERGAN

Protocol 199201-010 Amd 3

Date (DD/MMM/YYYY)/Time (PT)

████████████████████

Signed by:

████████████████████

Justification

████████████████████

2.2 List of Figures

| | |
|------------|------------|
| [REDACTED] | [REDACTED] |
|------------|------------|

3. List of Abbreviations and Definition of Terms

Table 3-1 Abbreviations and Definitions of Terms

| Abbreviation/Term | Definition |
|-------------------|--|
| AE | adverse event |
| AGN | Allergan |
| ANCOVA | analysis of covariance |
| ANOVA | analysis of variance |
| ATC | Anatomical Therapeutic Chemical |
| CFB | change from baseline |
| CMH | Cochran-Mantel-Haenszel |
| DCNVA | distance corrected near visual acuity |
| eCRF | electronic case report form |
| GCP | Good Clinical Practice |
| ICH | International Conference on Harmonisation |
| IOP | intraocular pressure |
| IxRS | interactive response system |
| LOCF | last observation carried forward |
| LS | least squares |
| MedDRA | Medication Dictionary for Regulatory Activities |
| mITT | modified intent-to-treat |
| N | number of patients |
| N/A | not applicable |
| NEI | national eye institute |
| NVPT | near vision presbyopia task |
| OC | observed cases |
| OCT | optical coherence tomography |
| OU | both eyes |
| PCS | potentially clinically significant |
| PICO PRO | presbyopia impact and coping questionnaire patient-reported outcome |
| PO | primary objective |
| PP | per-protocol |
| PPSQ PRO | presbyopia patient satisfaction questionnaire patient-reported outcome |
| PRO | patient-reported outcome |
| PT | preferred term |
| QD | once daily |
| SAE | serious adverse event |
| SADE | serious adverse device effect |
| SAP | statistical analysis plan |
| SD | standard deviation |
| SE | standard error |
| SO | secondary objective |
| SOC | system organ class |
| TEAE | treatment-emergent adverse event |
| UDVA | uncorrected distance vision acuity |
| UNVA | uncorrected near vision acuity |
| VAS | visual analog scale |

| Abbreviation/Term | Definition |
|-------------------|---|
| [REDACTED] WHO | [REDACTED] World Health Organization |

4. Introduction

This statistical analysis plan (SAP) details comprehensive, technical specifications of the statistical analyses of the efficacy, safety data and health outcomes outlined and/or specified in the final protocol of Study 199201-010 (version dated 2015-10-28) and the most recent amendment (version 3 dated 2016-08-18). Specifications of tables, figures, and data listings are contained in a separate document. The SAP for pharmacokinetic/pharmacodynamic and/or health economics and outcomes research data will be prepared separately. This document is organized into 3 main sections:

1. Study overview
2. Statistical Methodology and Study Endpoints
3. Data Handling and Analysis Conventions

4.1 Study Design Summary

This multicenter, double-masked, randomized, parallel-group, vehicle-controlled study will be a controlled comparison of fixed combinations of AGN-199201 and AGN-190584 at different concentrations to vehicle dosed in both eyes (OU), and the fixed combination of AGN-199201 [REDACTED] and AGN-190584 [REDACTED] dosed in OU or in the nondominant eye only. Study medication will be administered once daily (QD) in the morning. During office visits 1 through 5, study medication will be administered at hour 0 (8 AM \pm 1 hour). Following the treatment period, all patients will be seen for a 14 ± 2 -day follow-up period as shown in [Figure 1](#). The study duration will be 38 to 65 days per patient.

[figure not shown]

Table 4-1 Study Treatment Group

| Treatment Group | AGN-199201 (%) | AGN-190584 (%) | Dosing |
|-----------------|-----------------|-----------------|-----------------|
| 1 | Vehicle control | Vehicle control | OU |
| 2 | ██████████ | ██████████ | OU |
| 3 | ██████████ | ██████████ | OU |
| 4 | ██████████ | ██████████ | OU |
| 5 ^a | ██████████ | ██████████ | Nondominant eye |

OU = both eyes

^a Dominant eye dosed with vehicle

[figure not shown]
4.2 Study Objectives

[figure not shown]
Each study primary objective (PO), and secondary objective (SO) are presented below:

Table 4-2 Study Objectives

[figure not shown]
| Objectives |
|--|
| PO To evaluate the safety, efficacy, and tolerability of fixed combinations of AGN-199201 and AGN-190584 over a 42-day observation period when administered bilaterally, once daily (QD) for 28 days in patients with presbyopia |
| SO1 To compare the safety, efficacy, and tolerability of a fixed combination of AGN-199201 ██████████ and AGN-190584 ██████████ when administered monocularly to the nondominant eye versus bilaterally over a 42-day observation period with QD dosing for the first 28 days in patients with presbyopia |
| SO2 To assess the systemic pharmacokinetics of AGN-199201 ██████████ and AGN-190584 ██████████ following single and multiple (QD for 28 days) ophthalmic administrations as a fixed combination in 1 or both eyes (OU) |
| SO3 To evaluate the psychometric properties of the de novo patient-reported outcome (PRO) instruments developed for this program, including the near vision presbyopia performance tasks and task-based questionnaire under mesopic and photopic conditions, the presbyopia patient satisfaction questionnaire, and the presbyopia impact and coping questionnaire |

[figure not shown]
PO = primary objective, SO1 = first secondary objective, SO2 = second secondary objective, SO3 = third secondary objective

[figure not shown]

[figure not shown]

[figure not shown]

[figure not shown]

5. Statistical Methodology and Study Endpoints

5.1 Statistical Methods Planned in the Protocol and Determination of Sample Size

This statistical analysis plan (SAP) will be approved prior to database lock. The SAP expands the statistical section of the protocol and contains a detailed description of methods to analyze data collected in the study. The text portion of the SAP will be included in the CSR report as Appendix 16.1.9.

5.1.1 Statistical and Analytical Plans

Statistical analyses will be conducted using [REDACTED]

5.1.1.1 Common Conventions

5.1.1.1.1 Analysis Populations

The analysis populations will consist of patients as defined below: See [Table 5-1](#).

Table 5-1 Analysis Populations

| Population | Definition | Study Treatment |
|---------------------------------|--|-----------------------|
| Screened | All screened patients who sign informed consent | — |
| Modified Intent-to-Treat (mITT) | All randomized patients with a baseline and at least 1 post baseline assessment of mesopic, high contrast, UNVA and will be analyzed as randomized | Randomized assignment |
| Safety | All patients who received ≥ 1 administration of study treatment and will be analyzed as treated | Actual received |

The efficacy variables will be analyzed using the mITT population. All safety measures will be analyzed using the safety population.

5.1.1.1.2 Study Treatments

The following treatment groups are defined for this study, also presented in [Table 4-1](#), as group 1, 2, 3, 4 and 5:

- Group 1: Vehicle Control, OU
- Group 2: Fixed combination AGN-199201 [REDACTED] and AGN-190584 [REDACTED]), OU
- Group 3: Fixed combination AGN-199201 [REDACTED] and AGN-190584 [REDACTED] OU
- Group 4: Fixed combination AGN-199201 [REDACTED] and AGN-190584 [REDACTED], OU
- Group 5: Fixed combination AGN-199201 [REDACTED] and AGN-190584 [REDACTED]),
Non-dominant eye and vehicle to the dominant eye

5.1.1.1.3 Statistical Methodology

The methodologies defined below apply as specified to individual endpoints defined in this SAP. When indicated, 95% two-sided confidence intervals and two-sided p-values will be presented. Individual endpoint analyses may specify exceptions (additions or deletions) to these general definitions.

Table 5-2 Statistical Methodology

| Methodology | Description |
|-----------------------------|---|
| M1 Categorical counts | 
 Number of patients in individual categories 
 Patients with ≥ 1 qualifying event counted once per individual category |
| M2 Categorical descriptives | 
 Number and percentage of patients in individual categories 
 Patients with ≥ 1 qualifying event counted once per individual category (Optional) N included if percentage denominator \neq number of patients in the population (standard percentage denominator). |
| M3 PCS descriptives | 
 Number and percentage of patients meeting potentially clinically significant (PCS) criteria 
 Patients with ≥ 1 qualifying event counted once per PCS category Percentage denominator = number of patients with non-missing baseline and ≥ 1 non-missing postbaseline assessment Unevaluable assessments considered missing |
| M4 Continuous descriptives | 
 N included, mean, standard deviation (SD), median, minimum, maximum N included = patients with non-missing value |
| M5 CFB descriptives | 
 Continuous descriptives for baseline, postbaseline, and change from baseline (CFB) values N included = patients with non-missing values at both baseline and the specified postbaseline analysis visit |
| M6 CFB ANCOVA | 
 Continuous descriptives and standard error (SE) for baseline, postbaseline, and CFB values Estimates derived from mixed model for CFB value controlling for treatment group and covariates (baseline UNVA severity, iris color and age group) 
 Least squares (LS) means and standard errors P-values and confidence intervals from contrast t-test comparing active AGN-199201 treatment groups vs AGN-199201 vehicle N included = patients with non-missing values at both baseline and the postbaseline analysis visit |
| M7 CFB figure | 
 Plot of CFB LS means and SE bars for each treatment group |
| M8 Responder | 
 Categorical descriptives for responders and nonresponders 
 Nonresponders include: 
 Patients who do not meet responder criteria CMH test comparing active AGN-199201 treatment groups vs AGN-199201 vehicle |

ANCOVA = analysis of covariance; N = number of patients. CMH = Cochran-Mantel-Haenszel
 Raw and derived data listings will be provided, and will be fully defined in the table, figure, and data listing specification document.

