5.4 Treatment Allocation Ratio and Stratification

Patients will be randomized in a 1:1:1:1:1 ratio into 1 of 5 treatment groups:

- Group 1: Vehicle control, OU
- Group 2: Fixed combination AGN 199201 (██████████) and AGN 190584 (██████████), OU
- Group 3: Fixed combination AGN 199201 (██████████) and AGN 190584 (██████████), OU
- Group 4: Fixed combination AGN 199201 (██████████) and AGN 190584 (██████████), OU
- Group 5: Fixed combination AGN 199201 (██████████) and AGN 190584 (██████████),
monocular dosing to the nondominant eye and vehicle to the dominant eye

Randomization will be stratified by age (2 groups: ≤ 50 and > 50) and iris color (2 groups: brown and not brown) at the baseline visit. There will be a total of 4 strata; brown eyes and age ≤ 50 years, brown eyes and age > 50 years, not brown eyes and age ≤ 50 years, and not brown eyes and age > 50 years. For the determination of stratification group assignment for each patient, sites will be required to enter iris color (ie, brown, blue, green, gray, or hazel) and age into the Interactive Response System (IxRS), and the IxRS will assign the stratum.

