7.3.1 Primary Efficacy Analyses

For the primary efficacy analysis, the weighted average change from baseline will be analyzed by ANCOVA with treatment group, age group, and iris color as fixed effects. A detailed algorithm for the derivation of the primary efficacy variables will be documented in the AP.

█ [REDACTED]

█ [REDACTED]

█ [REDACTED]

█ [REDACTED]

Approval Date: 18-Aug-2016

[Redacted text block]

[Redacted text block]

[Redacted text block]

[Redacted text block]

[Redacted text block]

[Redacted text block]

[Redacted text block]

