7.4 Subgroup Analyses

Subgroup analyses will be performed for the primary efficacy variable by UNVA at baseline (20/40 to 20/80 and 20/100 to 20/200), age group, and iris color (brown or not brown).

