5.1.1.2.5 Baseline Characteristics

Baseline characteristics will be summarized in total and by treatment group for the mITT and Safety populations as follows:

Table 5-8 Baseline Characteristics Summaries

| Parameter | Description | Timing | Methodology |
|--------------------------|--|----------------------|-------------|
| Baseline characteristics | 
 • Iris color | Latest assessment in | Categorical |

| Parameter | Description | Timing | Methodology |
|----------------------|---|---|--------------------------|
| | | Screening Period or Pretreatment Period | descriptives |
| Randomization strata | 
 UNVA severity at baseline ($\leq 20/80$ and $> 20/80$) | Randomization date | Categorical descriptives |
| Baseline efficacy | 
 Mesopic pupil diameter with Grand Seiko sites vs without Grand Seiko sites UNVA severity at baseline with Grand Seiko sites vs without Grand Seiko sites | Randomization date | Continuous descriptives |

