5.1.1.3.2 Mesopic, High Contrast UNVA

[figure not shown]
Mesopic, high contrast UNVA endpoints will be summarized by treatment group for mITT Population.

[figure not shown]
Table 5-14 Mesopic, High Contrast UNVA

| Endpoint | Description | Timing | Methodology |
|--|--|-------------------------|------------------------------------|
| Average change from baseline in UNVA letters (Primary efficacy variable) | Average change from baseline in UNVA lines in the nondominant eye at day 28. | Treatment Period Day 28 | CFB ANCOVA ¹ CFB figure |
| [Redacted] | [Redacted] | [Redacted] | [Redacted] |
| [Redacted] | [Redacted] | [Redacted] | [Redacted] |

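### The protocol and SAP specify different primary ANCOVAs: the SAP adds baseline UNVA severity, visibly defined only as a 20/80 split; fix one model with a linear baseline term in both.

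*SAP*

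**What the plan says.** Protocol 7.3.1: the primary variable is "analyzed by ANCOVA with treatment group, age group, and iris color as fixed effects". In the visible protocol, baseline UNVA enters the analysis only as a subgroup factor, in 7.4: "UNVA at baseline (20/40 to 20/80 and 20/100 to 20/200".

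SAP 5.1.1.1.3, Table 5-2, method M6 (CFB ANCOVA): "Estimates derived from mixed model for CFB value controlling for treatment group and covariates (baseline UNVA severity, iris color and age group". Table 5-14 assigns M6 to the primary variable: "Average change from baseline in UNVA lines in the nondominant eye at day 28". The method entry carries a footnote whose text is not visible. The SAP also allows overrides by endpoint: "Individual endpoint analyses may specify exceptions (additions or deletions) to these general definitions".

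SAP Table 5-8 has a row headed "Randomization strata" containing UNVA severity cut at 20/80. The next row lists "UNVA severity at baseline with Grand Seiko sites vs without Grand Seiko sites" under continuous descriptives. Protocol 5.4 says of the strata: "There will be a total of 4 strata", formed by age group and iris color.

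SAP 5.2.2 lists three changes: the renamed primary endpoint, an added 2-line responder analysis, and no subgroups by gender, race or ethnicity. SAP section 4 states that it follows protocol amendment 3.

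**The concern.** Both documents describe the primary analysis, but their lists of model terms differ. M6 does not say whether baseline UNVA severity is a class or a measurement, nor which lighting condition or eye it comes from. M6 also calls the model mixed, where the protocol has fixed effects only.

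An analyst could therefore fit no baseline term (protocol), the 20/80 split (the likeliest reading of the SAP) or a linear term. Each gives a different estimate and interval for the same active-versus-vehicle contrast. The first two also give up precision if change depends roughly linearly on baseline. The stratum label adds confusion, because it makes a covariate that randomization did not balance look like a design factor.

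**Working it through.** **1. The model terms side by side**

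| Source | Terms besides treatment | Baseline UNVA |
|---|---|---|
| Protocol 7.3.1 | age group, iris color | none |
| SAP M6 | age group, iris color, baseline UNVA severity | form not given in M6 |
| SAP Table 5-8 | (descriptive table) | two classes at 20/80; also named in a row with continuous descriptives |
| Protocol 5.4 strata | age group, iris color | none |

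**2. The plan's own power figure** (inputs: protocol 7.5 and SAP 5.1.2; 26 per arm, two-sided 0.05, age weights 2/3 and 1/3)

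- Effect: (2/3)(1.98) + (1/3)(0.72) = 1.56 lines.
- Active variance within age: (2/3)(1.12²) + (1/3)(1.87²) = 2.00. Adding the spread in effect between age groups, (2/3)(1/3)(1.98 − 0.72)² = 0.35, gives 2.35.
- Vehicle variance: (2/3)(1.01²) + (1/3)(1.15²) = 1.12.
- Common SD: √[(2.00 + 1.12)/2] = 1.25, or √[(2.35 + 1.12)/2] = 1.32.
- Power by two-sample t: 99.3% or 98.7%. The stated 99% reproduces, and it uses no baseline covariate.

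**3. Gain from a linear baseline term** (the documents give no correlation; r is an assumed partial correlation of baseline with change, within treatment, age group and iris color)

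- If baseline and Day 28 variances are equal, r = √[(1 − ρ)/2], with ρ the baseline-to-Day 28 correlation. So r = 0.2 means ρ = 0.92, and r = 0.6 means ρ = 0.28.
- Linear versus none: 1/(1 − r²).
- Linear versus split: (1 − e·r²)/(1 − r²), where e is the share of baseline variance that the split keeps.
- For e, assume 8 equal acuity steps from 20/40 to 20/200, four on each side of the cut. Flat, half worse than 20/80: 4/5.25 = 0.76. Flat within class, a quarter worse: 3/4.25 = 0.71. Bell-shaped, a quarter worse: 0.59 to 0.67.

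The table shows relative sample size. The simulation fits a five-arm common-variance ANCOVA with 17 younger and 9 older patients per arm. It uses the planning SDs, gives all four active arms the earlier study's effect and SD, and takes e = 0.71 and 0.76.

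| r | v none, formula | v none, simulated | v split, formula (e = 0.76 / 0.71 / 0.59) | v split, simulated |
|---|---|---|---|---|
| 0.1 | 1.01 | – | 1.00 / 1.00 / 1.00 | – |
| 0.2 | 1.04 | 1.03 | 1.01 / 1.01 / 1.02 | 1.01 |
| 0.4 | 1.19 | 1.16–1.17 | 1.05 / 1.06 / 1.08 | 1.05 |
| 0.6 | 1.56 | 1.47–1.51 | 1.13 / 1.17 / 1.23 | 1.11–1.16 |

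If the true baseline effect were a pure step at 20/80, the last formula would apply in reverse, and the split would gain about 1-17%.

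**4. What this means in lines** (same simulation, r from 0.2 to 0.6)

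- 95% CI half-width: 0.76 with no baseline term; 0.75 falling to 0.66–0.67 with the split; 0.75 falling to 0.63 with the linear term.
- SD of the difference between two models' estimates of one contrast: 0.08–0.22 (none v linear), 0.07–0.19 (none v split), 0.04–0.12 (split v linear), against a planned effect of 1.56.
- Simulated power: none 98.4–98.7%, split 98.7–99.7%, linear 98.8–99.9%. Analytic power for a common-variance model with no baseline term is 97.0–99.1%.

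**The case against.** The strongest reply is that the form may be stated where this copy does not show it. The Table 5-14 footnote is attached to the primary method, M6 permits exceptions, and text around the efficacy tables is removed. A reader might infer that the plan never says how the covariate enters; the documents do not support so flat a statement. What can be said is that M6 gives no form and that the visible text defines the term once, as a split.

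That visible text does lean towards the split. It matches the protocol 7.4 classes, and M6 lists the term beside two binary factors. The continuous row in Table 5-8 is weak evidence for a second form, because one cell there also covers pupil diameter. This stands: the split is the likeliest reading.

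It is also fair that a prespecified split would remove the ambiguity, and that the documents do not dictate a linear term. The case for linear is efficiency: the Day 1 hour 0 value is already required for the change score, and the term costs the same 1 degree of freedom.

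Finally, a SAP may expand a protocol, and this one is to be approved before database lock. Section 5.2.2 is not a clean list of departures from amendment 3 either, since amendment 3 had already dropped the subgroups it mentions. So the missing entry is a documentation gap, not evidence of an uncontrolled analysis. It still leaves two primary models on file.

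**Conclusion.** The concern holds as a mismatch between protocol and SAP, with an available gain in precision. Three points stand whatever the hidden footnote says: the two documents list different primary model terms, the visible 5.2.2 does not record the added covariate, and Table 5-8 calls a UNVA split a randomization stratum.

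For an assumed r of 0.2 to 0.6 and a roughly linear baseline effect, the linear term is worth about 3-50% more patients than no baseline term. Against the split it is worth about 1-16% by simulation, and up to 23% by formula for a bell-shaped baseline. At r = 0.1 the gain is about 1% or less, and a pure step at 20/80 would favour the split.

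Two stronger inferences are not supported. The first is that the primary comparison is at risk: power is about 97-99% or higher under every model, and the sample size does not change. The second is that patients were stratified by UNVA: protocol 5.4 is explicit, and the label sits in a descriptive table.

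**What to change.** - In SAP M6 (or the primary row of Table 5-14) and in protocol 7.3.1, specify one fixed-effects ANCOVA: change from baseline in lines = treatment + age group + iris color + Day 1 hour 0 mesopic, high contrast UNVA of the nondominant eye. Enter baseline as a linear term on the outcome's scale: lines, not the Snellen denominator. State the unit explicitly, because the primary row of Table 5-14 names both letters and lines.
- Replace the mixed-model wording in M6 accordingly.
- Keep the 20/80 split for the protocol 7.4 subgroup analysis.
- Record the added covariate in SAP 5.2.2.
- In Table 5-8, show age group and iris color as the randomization strata and move UNVA severity to the baseline characteristics.

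The cost is wording and one line of code. No new data are needed, and the linear term uses 1 degree of freedom, as the split does. The change should be made before database lock.
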